8.3.2 Estimated glomerular filtration rate (eGFR)

The eGFR to determine eligibility of the patient for screening into the trial will be calculated at Visit 1 from the serum creatinine concentration measured at the local laboratory. The eGFR will be further calculated from creatinine concentration measured at Visits 2, 3, 5, 7, 11, 13, 15, and 16 (randomization, Weeks 1, 4, 8, 24, 40, 56, and 68), and end of study (Week 84) at the central laboratory. The eGFR calculation will be based on the Abbreviated Modification of Diet in Renal Disease (MDRD) study equation ([Levey, et al 2007](#)).

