Physical examination	
A complete physical exam will be performed at Visits 1, 5, 7, 11, 13, 15, 16 and 17 (physical exam at visit 2 to be performed only if randomization visit is done on a different calendar date than screening). It will include the examination of general appearance, skin, neck, eyes, ears, nose, throat, lungs, heart, abdomen, back, lymph nodes, extremities, and vascular and neurological examinations. If indicated based on medical history, and/or symptoms, rectal, external genitalia, breast and pelvic exams will be performed.
 
Information for all physical examinations must be included in the source documentation at the study site (with the exceptions of pandemic-related virtual visits mentioned above). Significant findings that are present prior to the informed consent must be included in the Relevant Medical History/Current Medical Conditions screen on the patient's eCRF. Significant findings made after informed consent which meet the definition of an adverse event must be recorded on the Adverse Event eCRF.

Vital signs	
Vital signs will be assessed at every in-person visit, and in cases where the COVID-19 pandemic limits or prevents on-site study visits,. This will include blood pressure and pulse measurements. BP will be measured using a standard sphygmomanometer with an appropriately sized cuff and the non-dominant arm in the sitting position after 5 minutes of rest. Every effort should be made to use the same arm for the patient for all vital signs assessments and where possible, the same person doing the assessment. For virtual visits, documentation of any vital signs available (e.g. home BP cuff results) should be recorded in the eCRF.

Height and weight	
Height in centimeters if possible will be measured at Visits 1 and 2. Body weight to the nearest 0.1 kg without shoes, will be measured at Visits 1, 2, 3, 5, 7, 11, 13, 15, 16 and 17.

Assessment	Specification
Waist/hip circumference	Waist/hip circumference to the nearest centimeter will be measured at Visit 1.

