The proportional change in hs-Troponin (high sensitivity) from baseline to Week 4 will be analyzed using an ANCOVA model similar to that of the primary efficacy analysis. Log-transformed hs-Troponin will be used for analysis. The analysis will be repeated for Week 8.

Analysis of secondary endpoint 6

The dosing level will be summarized by treatment group and in-/out-of-hospital randomization status. Incidence of discontinuations (all causes) will be summarized by treatment group and in-/out-of-hospital randomization status.

Analysis of secondary endpoint 7

Incidence of event will be analyzed using logistic regression model with treatment and in/out-of-hospital randomization as fixed factors. The model will be used to estimate the odds ratio for treatment and its 95% confidence interval.

The number (and proportion) of patients with adverse events of special interest will be summarized by treatment, primary system organ class and preferred term. All these secondary endpoints will be analyzed using FAS and nominal p-values will be reported. There will be no adjustment for multiplicity.

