### 2.2.1 Subgroups of interest

The following subgroups will be analyzed for the primary endpoint and for selected secondary endpoints based on clinical decision:

1. Age group ( $< 65, \geq 65$  years) and ( $< 75, \geq 75$  years)
2. Left ventricular ejection fraction (LVEF) categories prior to randomization:
  - $> 40$  to  $< 45\%$  vs.  $\geq 45\%$ ;

- > 40 to < 50% ((HFmrEF (mildly reduced) ), ≥ 50% ( (HFpEF) preserved )
- ≥ 50 to ≤ 60% vs. >60\*
- >40 to ≤60 vs. > 60\*
- ≤ median vs. > median

3. Prior use of ACEi/ARB (at the time of hospitalization)
4. Four groups defined by the Baseline quartiles of NT-proBNP
5. Baseline eGFR (< 45, 45 to < 60, ≥ 60 ; <30 or ≥ 30 mL/min/1.73 m^2)
6. SBP at randomization (< 110, ≥ 110 mm Hg)
7. Race
8. Ethnicity
9. Atrial fibrillation (AF) vs. no AF at the time of consent
10. Body mass index (BMI) ≥ 30 vs. BMI < 30; BMI ≤50 vs. >50 kg/m^2
11. Sex
12. New onset HF (at the time of hospitalization) – ‘de novo heart failure’
13. New York Heart Association (NYHA) class at randomization
14. Recovered EF / Improved EF (HFimpEF) (most recent left ventricular ejection fraction (LVEF) > 40% (within past 3 months), but history of prior documented LVEF < 40%)
15. Time from presentation to hospital (if applicable) to randomization time
16. Prior history of HF
17. Prior Hospitalization for Heart Failure
18. Duration of Heart Failure (< 12 months, 12-24 months, 24-60 months, and > 60 months)
19. In-hospital/out-of-hospital randomization status
20. Structural heart disease (yes/no)
21. Subjects without COVID-19 positive during the trial.
22. Enrollment Country: Canada vs United States

\* LVEF of >60% is defined as normal; LVEF <= 60% is defined as “below normal”

See [Sections 2.5](#) and [2.6](#) for further details on the primary and secondary objectives, respectively.

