### **2.6.2.7 Analysis of secondary endpoint 7**

Incidence of below adverse events of special interest (AESI) during treatment will be considered.

- Incidence of symptomatic hypotension (Collected in AESI CRF)
- Incidence of hyperkalemia (potassium >5.5 mEq/L) (Collected in AESI CRF)
- Incidence of angioedema (Collected in AESI CRF)
- Incidence of worsening renal function, defined as an increase in serum creatinine of  $\geq 0.5\text{mg/dl}$  and worsening of the eGFR by at least 25% [using Central Lab data from same scheduled or unscheduled visits]

Incidence of adverse events of special interest (AESIs) will be analyzed using a logistic regression model with treatment and in-hospital/out-of-hospital randomization as fixed factors. The model will be used to estimate the odds ratio for treatment and its 95% CIs.

- The number (and proportion) of subjects with AESI will be summarized by treatment.
- The primary analysis of secondary endpoint 7 will be repeated but data that occurs after diagnosis as COVID-19 positive will be censored at the subject level.

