#### **Chemistry**

Assessments required for eligibility that need to be measured at Visit 1 include creatinine, potassium, and total bilirubin. Blood urea nitrogen (BUN), glucose, creatinine, total bilirubin, AST (SGOT), ALT (SGPT), alkaline phosphatase, sodium, potassium, chloride, calcium, total protein, albumin, uric acid, and lipid profile be measured at Visits 1 (local lab), 2, 3, 5, 7, 9, 11, 13, 15, 16 and 17 (central lab).

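### The endpoint 7 logistic models omit baseline potassium, systolic pressure and eGFR, which are already collected; adding one matching covariate to each would gain a little power at almost no cost

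*SAP*

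**What the plan says.** SAP 2.6.2.7 models each adverse event of special interest (AESI) with two terms: "Incidence of adverse events of special interest (AESIs) will be analyzed using a logistic regression model with treatment and in-hospital/out-of-hospital randomization as fixed factors". It reports the result on the odds-ratio scale: "The model will be used to estimate the odds ratio for treatment and its 95% CIs". Protocol 12.5.1 matches: "Incidence of event will be analyzed using logistic regression model with treatment and in/out-of-hospital randomization as fixed factors".

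The three relevant baseline values are part of routine data collection:

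- **Potassium.** In the SAP chemistry schedule: "sodium, potassium, chloride, calcium, total protein, albumin, uric acid, and lipid profile be measured at Visits 1 (local lab), 2, 3, 5". Visit 2 is the randomization visit.
- **eGFR.** Protocol 8.3.2: "The eGFR will be further calculated from creatinine concentration measured at Visits 2, 3, 5, 7, 11, 13, 15, and 16", at the central laboratory.
- **Systolic pressure.** Protocol Table 8-2: "Vital signs will be assessed at every in-person visit".

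Two of the three are already subgroup variables in SAP 2.2.1: baseline eGFR, and systolic pressure, listed as "SBP at randomization (< 110, ≥ 110 mm Hg". That list applies to the primary endpoint and, by clinical decision, to selected secondary endpoints. It does not put a covariate into the endpoint 7 model. Nothing in the text available adds any of the three to that model or explains their absence.

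By contrast, the primary ANCOVA (SAP 2.5.2) includes the log baseline value of its own outcome. Randomization is unstratified (SAP 1.1). SAP 2.6.1 makes the secondary p-values nominal, without multiplicity adjustment.

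**The concern.** Each of the three events is tied to a quantity known before the first dose.

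- **Hyperkalemia** is an absolute threshold, above 5.5 mEq/L. Entry excludes only potassium above 5.2, so a patient can start 5.5 − 5.2 = 0.3 mEq/L from the event.
- **Worsening renal function** needs a creatinine rise of at least 0.5 mg/dL together with a 25% fall in eGFR. For illustration, a 0.5 rise is 0.5/0.8 = 62.5% of a baseline of 0.8 but 0.5/2.0 = 25% of a baseline of 2.0. How hard the event is to reach therefore depends on where the patient starts.
- **Symptomatic hypotension** plausibly depends on starting systolic pressure, which the stability criteria bound only from below, at 100 mmHg.

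A logistic model that omits a prognostic covariate estimates an odds ratio closer to 1 and has less power. In a comparison of harms that is the unhelpful direction, because a real difference is somewhat more likely to be reported as not significant.

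**Working it through.** **1. The plan's own power figure.** The only one is for the primary endpoint (SAP Section 3): 450 patients, 1:1, 23% reduction, SD 0.85, 15% missing, two-sided 0.05, 85% power.

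- Evaluable per arm: 450 × 0.85 / 2 ≈ 191.
- SE = 0.85 × √(2/191) = 0.0870; effect = |ln 0.77| = 0.2614; ratio = 3.005.
- Power ≈ Φ(3.005 − 1.960) = 85.2% (85.0% with the t distribution).

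The stated 85% is reproduced. Endpoint 7 has no stated power, event rate or precision target, so there is nothing to reproduce for it.

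**2. Effect of adding a baseline covariate.** From the documents: 225 per arm, two-sided 0.05, the two-term logistic model. **Assumed:** event rates, and the covariate odds ratio (OR) per SD. Each scenario used 3,000 simulated trials, and both models were fitted to the same trials. Power is shown as planned model → model with the covariate:

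| Rates, control / treated | OR 1.5 per SD | OR 2 per SD | OR 3 per SD |
|---|---|---|---|
| 5% / 11% | 66.2 → 66.6% | 65.2 → 66.4% | 64.7 → 68.6% |
| 10% / 18% | 68.4 → 70.1% | 69.1 → 71.3% | 66.6 → 73.5% |
| 15% / 25% | 74.9 → 76.0% | 76.2 → 79.6% | 76.1 → 83.3% |
| 20% / 30% | 69.3 → 70.2% | 68.1 → 71.7% | 69.0 → 76.8% |

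The gain runs from 0.4 points (66.6 − 66.2) to 7.8 points (76.8 − 69.0). A covariate with no prognostic value changed power by at most 0.3 points.

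**3. Validity.** With 15% in both arms, the planned model rejected in 4.7% to 5.2% of trials and the adjusted model in 5.0% to 5.1%. Both hold the nominal level.

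**4. Where the gain comes from.** Take 15% / 25% with OR 3 per SD:

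- Planned: log OR 0.652, SE 0.244, ratio 0.652/0.244 = 2.67, OR = e^0.652 = 1.92.
- Adjusted: log OR 0.771, SE 0.267, ratio 0.771/0.267 = 2.89, OR = e^0.771 = 2.16.

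The SE rises, but the estimate moves further from zero than the SE grows. Across the non-null scenarios the SE rose by about 1–2% (OR 1.5), 2–5% (OR 2) and 5–11% (OR 3). A true variance reduction appears only on a marginal scale: the variance of a standardised risk difference fell by 1–2%, 3–8% and 8–17% respectively. The SAP does not plan that measure.

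**5. A second parameterisation.** A latent-normal simulation used a correlation between baseline and the event's underlying scale, with 225 per arm and assumed rates including 15% vs 24%. It gave gains of about 1 to 3 points at correlation 0.3, 5 to 7 at 0.5, and 11 to 15 at 0.7. At 15% incidence, 0.5 corresponds to an odds ratio of about 2.9 per SD, in line with the right-hand column above. A correlation of 0.7 corresponds to about 5.9 per SD, which is hard to defend here.

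**The case against.** The strongest reply is that this is a preference about efficiency. Most of that stands.

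- **A reader might infer that the plan loses precision.** On the scale the SAP reports it does not. The odds ratio is non-collapsible, so adjustment slightly widens its interval. The comparison with the primary ANCOVA carries over only in part, because in a linear model a baseline covariate does reduce the SE.
- **A reader might infer bias from chance imbalance, given unstratified randomization.** With 225 per arm, a one-SE imbalance is √(2/225) = 0.094 SD. At a covariate odds ratio of 2 to 3 per SD that shifts the treatment odds ratio by about 7% to 11%. This is ordinary sampling variation, already covered by the interval, and the null results show the test is sound.
- **A reader might infer that these odds ratios are the only modelled answer on tolerability.** That cannot be verified. Appendix B cites SAP 2.12.1 and 2.12.2, which are not in the public text, and it also models worsening renal function on pooled data.
- **The link may be weak.** Entry limits narrow all three covariates: potassium not above 5.2, eGFR at least 20, systolic pressure at least 100. Hyperkalemia and hypotension are collected on an AESI form, so they are not purely a value crossing a line. Worsening renal function is already defined as a change from baseline. Dose adjustment also responds to these measures.
- **The stakes are modest.** No decision rests on endpoint 7 significance. Counts, exposure-adjusted rates and shift tables also describe harm.
- **A short model is safer when events are few.** This is correct, and the fix must provide for it.

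What remains is that a prognostic value already in the database is left unused, that using it costs essentially nothing, and that an uninformative one would do no visible harm.

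**Conclusion.** The point holds as a cheap improvement. The two-term models are valid, but they give up some power and report odds ratios nearer 1 than models that also condition on the matching baseline value. Under assumed event rates and covariate strengths the gain is about 0.4 to 8 points: 0.4–2 at an odds ratio of 1.5 per SD, 1–4 at 2, and 4–8 at 3. The documents supply neither input, so the size cannot be fixed more closely and could be near zero. They do not support calling the omission an error, a source of bias, or a cause of wider intervals. Priority is low because the p-values are nominal.

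**What to change.** Before database lock, amend SAP 2.6.2.7 to add one continuous covariate to each of three models, using the baseline definition in SAP 2.1.1:

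- potassium for hyperkalemia;
- systolic pressure for symptomatic hypotension;
- eGFR for worsening renal function.

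In the same text:

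- keep treatment and in/out-of-hospital status, and state that the odds ratio is conditional on the baseline value;
- keep the two-term model for angioedema and for any AESI below an event-count threshold set in advance;
- keep the planned counts and proportions by arm as the unadjusted summary;
- say whether the pooled worsening-renal-function analysis in Appendix B, which borrows this model, changes too;
- record the departure from protocol 12.5.1 in SAP Section 4.

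The cost is a few lines of text and one model term each, with no new data. There are two drawbacks: patients without a baseline value leave the model, and the odds ratio is conditional on one more variable. Fixing the covariates while blinded also removes any later temptation to choose them after seeing an imbalance.

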### **2.6.3 Handling of missing values/censoring/discontinuations**

The analysis will be performed based on all available data in the FAS and based on likelihood method with an assumption of missing at random for missing data.

## **2.7 Safety analyses**

For all safety analyses, the SAF will be used. All listings and tables will be presented by treatment group and in-hospital/out-of-hospital randomization category.

Safety summaries (tables, figures) include only data from the on-treatment period with the exception of Baseline data, which will also be summarized where appropriate (eg, change from Baseline summaries). In addition, a separate listing for death including on-treatment and post treatment deaths will be provided. In particular, summary tables for AEs will summarize only on-treatment events, with a start date during the on-treatment period (treatment-emergent AEs (TEAEs)). The on-treatment period lasts from the date of first administration of study treatment to the last study visit.

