9.1 Discontinuation

9.1.1 Discontinuation of study treatment

Discontinuation of study treatment for a patient occurs when study treatment is stopped earlier than the protocol planned duration, and can be initiated by either the patient or the investigator.

The investigator must discontinue study treatment for a given patient if he/she believes that continuation would negatively impact the patient's well-being.

Study treatment must be discontinued under the following circumstances:

- Patient/guardian decision
- Pregnancy
- Use of prohibited treatment as per recommendations in the prohibited treatment section
- Any situation in which study participation might result in a safety risk to the patient
- Following emergency unblinding
- Any severe suspected drug related AE at the investigator's discretion

- Suspected occurrence of angioedema. A patient with any signs or symptoms of clinically significant angioedema should be thoroughly evaluated by the investigator to determine if it constitutes a reason for discontinuation of study medication.
- Depending on the serum potassium, blood pressure, or eGFR, patient may need to have their study drug dose or the dose of another concomitant medication reduced or discontinued; or, if appropriate, have potentially contributing agents adjusted. Refer to appendices for treatment guidelines for hyperkalemia, hypotension or renal dysfunction, respectively.

If discontinuation of study treatment occurs, the investigator should make a reasonable effort to understand the primary reason for the patient's premature discontinuation of study treatment and record this information.

Patients who discontinue study treatment or who decide they do not wish to participate in the study further should NOT be considered withdrawn from the study UNLESS they withdraw their consent (see withdraw of informed consent section.). **Where possible, they should return for the assessments indicated** in the assessment schedule. If they fail to return for these assessments for unknown reasons, every effort (e.g. telephone, e-mail, letter) should be made to contact the patient/pre-designated contact as specified in the lost to follow-up section. This contact should preferably be done according to the study visit schedule.

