- Drug interrupted/withdrawn

6. its outcome (i.e. recovery status or whether it was fatal)

Conditions that were already present at the time of informed consent should be recorded in medical history of the patient.

Adverse events (including lab abnormalities that constitute AEs) should be described using a diagnosis whenever possible, rather than individual underlying signs and symptoms.

Adverse event monitoring should be continued for at least 30 days following the last dose of study treatment.

Once an adverse event is detected, it must be followed until its resolution or until it is judged to be permanent (e.g. continuing at the end of the study), and assessment must be made at each visit (or more frequently, if necessary) of any changes in severity, the suspected relationship to the interventions required to treat it, and the outcome.

Information about adverse drug reactions for the investigational drug can be found in the Investigator's Brochure (IB).

Abnormal laboratory values or test results constitute adverse events only if they fulfill at least one of the following criteria:

- they induce clinical signs or symptoms
- they are considered clinically significant

- they require therapy

Clinically significant abnormal laboratory values or test results must be identified through a review of values outside of normal ranges/clinically notable ranges, significant changes from baseline or the previous visit, or values which are considered to be non-typical in patients with the underlying disease. Alert ranges for laboratory and other test abnormalities are included in [Appendix 1](#).

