For participants recruited under the Protocol Version 00 (Original Protocol) who do not continue in amendment protocol assessments performed at Weeks 10 or 12 (including, but not limited to, vital signs) are assigned to the open label phase for summarization purposes, unless otherwise noted. Unscheduled assessments are not assigned to a study phase for purposes of by-visit summaries.

For summarization of AEs, notable vital signs and laboratory abnormalities, and symptomatic hypotension by study phase, an assessment during the open label phase is defined as any assessment obtained in the following time interval:

After the date of the Week 8 visit. For participants without a Week 8 visit, a projected Week 8 visit date will be derived relative to their treatment start date.

Participants enrolled under Protocol Version 00 (Original Protocol) who died, withdrew consent, or were lost to follow-up prior to or on their projected Week 8 visit date will be excluded from the open-label phase.

End of Study (EOS)

EOS is obtained directly from the source data. A subject can discontinue treatment (EOT) at any time but continue the study, then the EOS is the study completion date. A subject who completes the study and has an EOS visit. If a subject discontinues the study for any reason, the discontinuation date is the EOS for that subject.

Follow-up for time-to-event analyses

For patients enrolled in the original protocol and continue to an open-label period, events are considered up to the end of their double-blind period (up to Week 8). For patients enrolled in Protocol Amendments 1-4, the events are considered up to their end of double-blind phase (EOS).

In-Hospital / Out-of-Hospital Randomization Status

The status for patient's in-hospital/out-of-hospital randomization is collected as "In-Patient or Out-Patient" category and will be provided by the Interactive Response Technology (IRT).

Year, month and week

For reporting purposes, the rules below will be followed to convert a year, month and week to days.

1 year = 365.25 days

1 month = 30.4375 days

1 week = 7 days

1 day = 24 hours

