### **2.7.1.2 General rules for AE reporting**

All information obtained on AEs will be displayed by treatment group and subject.

The number (and percentage) of subjects with TEAEs (events started after the first dose of study medication, or events present prior to start of double-masked treatment but increased in severity based on PT) will be summarized in the following ways:

- By treatment, primary SOC and PT.
- By treatment, primary SOC, PT and maximum severity.
- By treatment, pre-defined topic of interest, primary SOC and PT.

Separate summaries will be provided for study medication-related AEs, serious adverse events (SAEs), and other significant AEs leading to discontinuation.

A subject with multiple adverse events within a primary SOC is only counted once towards the total of the primary SOC.

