### **2.7.1.3 Treatment-emergent adverse events**

AE summaries will include all TEAEs. TEAEs are defined as AEs starting on or after the first day of study treatment. All AEs will be listed. AEs starting prior to the first day of study treatment (non-TEAEs) will be flagged in the listings.

All TEAEs will be summarized by study phase as defined in [Section 2.1.1](#).

TEAEs will be summarized by presenting the number and percentage of subjects having at least 1 TEAE, having at least 1 TEAE in each primary SOC, and for each PT using MedDRA coding.

A subject with multiple occurrences of a TEAE will be counted only once in the AE category.

Separate summaries will be presented by SOC, PT and severity. A subject with multiple severities for an AE will be summarized under the worst severity recorded for the event.

Any information collected will be listed as appropriate.

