#### **2.7.1.6 Exposure Adjusted Adverse Events**

The following Exposure adjusted incidence rate of adverse events will be presented by study phase and treatment group:

- Exposure-adjusted incidence rate of adverse events by preferred term

- Exposure-adjusted incidence rate of study treatment related adverse events by primary system organ class and preferred term
- Exposure-adjusted incidence rate of adverse events leading to permanent study treatment discontinuation by primary system organ class and preferred term
- Exposure-adjusted incidence rate of serious adverse events by primary system organ class and preferred term
- Exposure-adjusted incidence rate of deaths by primary system organ class and preferred term

The exposure adjusted incidence rate (IR) will be derived by the number of subjects with an event divided by the corresponding sum of the exposure duration for all subjects, where duration of exposure in Subject Treatment Years (STY) is counted up to the first qualifying event (or end of time at risk for subjects without event).

Incidence rate will be set to the 100 STY and only on treatment events (TEAE) will be included.

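### The safety on-treatment period ends at the last study visit rather than being tied to the last dose, so off-drug events can count as on-treatment and part of the 30-day post-dose window can be missed; time at risk is undefined and treatment-emergent has conflicting definitions.

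*SAP*

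**What the plan says.** **Period.** SAP 2.7 and protocol 12.5.2 both say: "The on-treatment period lasts from the date of first administration of study treatment to the last study visit". The tables are restricted to it: "summary tables for AEs will summarize only on-treatment events, with a start date during the on-treatment period".

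**Follow-up after stopping drug.** The End of Study definition in SAP 2.1.1 allows for it: "A subject can discontinue treatment (EOT) at any time but continue the study, then the EOS is the study completion date". Protocol 9.1.1 says of patients who discontinue treatment: "Where possible, they should return for the assessments indicated". Protocol 6.4.1, however, asks a patient whose drug is stopped completely to come back promptly for an end of study visit.

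**Rates.** SAP 2.7.1.6 gives incidence per 100 Subject Treatment Years, using on-treatment events only. For the denominator, "duration of exposure in Subject Treatment Years (STY) is counted up to the first qualifying event", or to the end of time at risk for patients with no event. Time at risk is not defined for safety.

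**Post-dose monitoring.** Protocol 10.1.1: "Adverse event monitoring should be continued for at least 30 days following the last dose of study treatment". Protocol 10.1.3 requires SAE reporting until 30 days after the last study visit.

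**Treatment-emergent.** SAP 2.7.1.2 and protocol 12.5.2 count events that start after the first dose and also "events present prior to start of double-masked treatment but increased in severity based on PT". SAP 2.7.1.3 says only: "TEAEs are defined as AEs starting on or after the first day of study treatment". It has no worsening limb and no end date.

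**The concern.** An on-treatment table is read as what happened while patients were exposed. Here the label covers all follow-up to the last visit. Protocol 6.1.4 and 6.1.5 bar open-label ACE inhibitors and ARBs during study treatment but allow them once the patient is withdrawn from it. Hyperkalemia, hypotension, renal decline or angioedema arising on such later therapy would be tabulated as an on-treatment event of the randomized arm. If stopping differs between arms, so does the off-drug share.

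The same definition cuts the other way for patients treated to the end. The period in which a delayed effect of the last doses would show, and which the protocol monitors, falls outside the tables.

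Two programmers following the SAP could also produce different rates, because time at risk is open, and different event counts, because treatment-emergent is not defined in one way.

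**Working it through.** The documents state no safety rate or exposure figure, so there is nothing to reproduce. The check has three parts.

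**1. Windows for example patients** (days from first dose; visit days from protocol Table 8-1)

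| Last dose | Last visit | Off-drug days counted as on-treatment | Days of the 30-day window left out |
|---|---|---|---|
| 588 | 588 | 0 | 30 |
| 56 | 56 | 0 | 30 |
| 570 | 588 | 18 | 12 |
| 28 | 588 | 560 | 0 |

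Over-inclusion and omission fall on different patients. At the 8-week minimum follow-up, the omitted window equals 30/56 = 54% of the on-treatment period.

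**2. Size of the off-drug share and its effect on rates**

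Inputs from the documents: 450 patients randomized 1:1, so 225 per arm (SAP 3), and an average study duration of about 46 weeks (protocol section 3). Assumed, because the documents give no values: a proportion q = 10–30% stop early, at a fraction f = 25–50% of their follow-up; the on-drug event rate is 20 per 100 years; the off-drug rate is 10, 20 or 40.

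- Person-time to last visit per arm: 225 × 46 × 7 / 365.25 = 198.4 patient-years.
- Off-drug share s = q(1 − f). Lowest: 0.10 × 0.50 = 5.0% (9.9 patient-years). Highest: 0.30 × 0.75 = 22.5% (44.6 patient-years).
- Denominator A ends at last dose, as treatment duration does in SAP 2.4.1: rate = on-drug rate + off-drug rate × s/(1 − s).
- Denominator B ends at the last visit, as the win-ratio time at risk does for a patient who completes (SAP 2.6.2.1.1): rate = on-drug rate × (1 − s) + off-drug rate × s.

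| Off-drug rate per 100 years | A: to last dose | B: to last visit |
|---|---|---|
| 10 | 20.5–22.9 | 19.5–17.8 |
| 20 | 21.1–25.8 | 20.0 |
| 40 | 22.1–31.6 | 21.0–24.5 |

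Each range runs from s = 5.0% to s = 22.5%; the true on-drug rate is 20. For simplicity, the formulas do not stop person-time at the first event. Under A, numerator and denominator cover different periods and the rate is too high. Under B they match, but treatment years include off-drug time, and the rate is too low, right or too high according to the off-drug rate.

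For patients treated to their last visit, the omitted window is (1 − q) × 225 × 30/365.25 = 12.9–16.6 patient-years per arm, or 6.5–8.4% of 198.4.

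**3. Treatment-emergent definitions side by side**

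Take an AE that begins between consent and first dose and worsens on drug. It counts under SAP 2.7.1.2 and the matching text in protocol 12.5.2. It does not count under SAP 2.7.1.3, or under the start-date rule in SAP 2.7 (also in protocol 12.5.2). An AE that starts after the last visit counts under SAP 2.7.1.3 read alone, but not under SAP 2.7.

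**The case against.** Counting safety events over the whole study is a recognised approach, and it is pre-specified in both documents. The double-blind phase in SAP 2.1.1 likewise runs to the Week 84 visit for amended-protocol patients. If time at risk carries its win-ratio meaning, numerator and denominator broadly agree. All of this stands as a defence of a whole-study table. It does not justify calling that table on-treatment, scaling it to treatment years, or leaving time at risk undefined.

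Stronger readings are tempting but not supported:

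- *Rates are overstated by a definite amount.* This needs a last-dose denominator, which SAP 2.7.1.6 does not state, and a discontinuation rate, which neither document gives.
- *Post-dose events disappear.* They do not. SAP 2.7.1.3 lists all AEs, SAP 2.7 lists post-treatment deaths, and protocol 10.1.3 keeps SAE reporting open. They are missing from the summary tables and rates.
- *Every patient loses the 30-day window.* Only those whose last dose is within 30 days of their last visit lose any of it.
- *Early stoppers typically add some 80 weeks off drug.* Stopping at Week 4 with follow-up to Week 84 is the extreme; average study duration is about 46 weeks. If protocol 6.4.1 is followed instead of 9.1.1, off-drug time shrinks and the omission grows.
- *Version 00 open-label events are mixed in throughout.* The phase rules in SAP 2.1.1 already separate that period in by-phase tables.

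The post-study telephone call might be argued to be the last visit. But it is not a numbered visit, and SAP 2.6.2.1.1 equates the last visit with the End of Study visit.

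The treatment-emergent conflict probably affects few events, because conditions present at consent go to medical history (protocol 10.1.1).

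**Conclusion.** The point holds as a defect of definition in the safety tables and exposure-adjusted rates. The on-treatment period is mislabelled, the rate denominator cannot be programmed uniquely, and the treatment-emergent rules conflict.

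Under the assumed stopping pattern, 5–22.5% of on-treatment time is off drug. Against an assumed true rate of 20 per 100 years, the tabulated rate would lie between 17.8 and 31.6, depending on the denominator and the off-drug event rate. These figures are illustrations, not predictions, and the documents do not fix the direction of bias. The amount of off-drug time also depends on how protocol 6.4.1 is reconciled with protocol 9.1.1 and SAP 2.1.1. The primary endpoint is not affected.

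**What to change.** - In SAP 2.7 and protocol 12.5.2, define on-treatment as first dose to last dose plus 30 days. Keep the SAP 2.1.1 phase rules that split off the Version 00 open-label period. For amended-protocol patients, let the double-blind phase end run to the same date, so that by-phase tables do not cut the window at Week 84.
- In SAP 2.7.1.6, define time at risk as that same period, for numerator and denominator alike.
- Keep whole-study tables as supportive, labelled as such.
- Use the SAP 2.7.1.2 treatment-emergent definition in SAP 2.7 and 2.7.1.3, and remove the conflict within protocol 12.5.2.
- Reconcile protocol 6.4.1 with protocol 9.1.1 and SAP 2.1.1 on follow-up after study drug is stopped.
- Record the change in SAP section 4.

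Cost: SAP wording, one extra set of tables and a change to the protocol sentence. No new data collection is needed, since the protocol already requires monitoring over the 30 days. The downside is that late off-drug events move to the supportive tables.
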